1.3.3 Rationale for Dosage and Route of Administration

The regimen of PXVX0317 selected for this study is 40 μ g of VLP with alum adjuvant administered in a single IM dose on Day 1. The alum dose of 300 μ g is within the range of doses of alum adjuvants used in many licensed vaccines, including VLP-based vaccines. This dose also creates a concentration ratio to PXVX0317 that achieves high (~90%) levels of adsorption, thought to enhance both immunogenicity and short-term stability. The IM route of administration is consistent with that in previous clinical studies (VRC 311 (13, 14), VRC 704 (15, 16), PXVX-CV-317-001, and EBSI-CV-317-002 (17)). This regimen was selected by an interim analysis of the PXVX-CV-317-001 study data. All regimens tested in PXVX-CV-317-001 were given to groups of 50 to 53 healthy adults and all resulted in 100% seroconversion by Day 57. The group receiving a single dose of 40 μ g plus alum showed the highest anti-CHIKV SNA GMT at Day 182 and Day 365.

The PXVX0317 vaccine (40 μ g CHIKV VLP + 300 μ g alum adjuvant) single dose has been selected for further development by the Sponsor in a planned Phase 3 clinical study (EBSI-CV-317-004).

2 STUDY OBJECTIVES AND PURPOSE

2.1 Primary Objectives

- To assess the induction of anti-CHIKV neutralizing antibody responses following a single adjuvant dose of PXVX0317 as measured 21 days (Day 22) after vaccination.
- To assess the induction of anti-CHIKV neutralizing antibody responses following a single adjuvant dose of PXVX0317 as measured 7 days (Day 8), 14 days (Day 15), and 56 days (Day 57) after vaccination.

2.2 Secondary Objective

- To assess the safety of a single dose of PXVX0317 in healthy adults.

2.3 Exploratory Objectives

- To obtain plasma and sera at Days 22 and 57 from subjects immunized with a single dose of PXVX0317 (40 µg CHIK VLP adjuvanted with 300 µg Alhydrogel) to support nonclinical studies.
- To characterize the kinetics of anti-CHIKV IgM, IgG, and neutralizing responses following a single dose of PXVX0317 as measured 7, 14, 21, and 56 days (Days 8, 15, 22, and 57) after vaccination.
- To characterize T and B-cell responses following a single dose of PXVX0317 with collections of PBMCs 7, 14, 21, and 56 days (Days 8, 15, 22, and 57 respectively) after vaccination.

3 STUDY DESIGN

3.1 Study Description

This is an open-label, single arm Phase 2 study in healthy adults 18 to 45 years of age. This study has a screening period of 30 days, a treatment and observation period from Day 1 to Day 22, and a follow-up period through Day 183. Subjects will receive CHIKV VLP at a dose of 40 µg in combination with 300 µg Alhydrogel on Day 1, have follow-up visits on Day 8, Day 15, and Day 22, with an additional plasmapheresis procedure and collection of serum on Day 22. A phone call follow-up visit will occur on Day 29, followed by a second plasmapheresis procedure and collection of serum at Day 57. A phone call follow-up visit to assess safety and concomitant medications will occur on Day 64. An EOS phone call follow-up visit to assess safety and concomitant medications will occur on Day 183.

3.1.1 Study Centers

This is a single center study in the US.

3.1.2 Number of Subject (Planned)

[figure not shown]
Twenty-five subjects are targeted for enrollment.

3.1.3 Estimated Study Duration

The per subject estimated total study duration is 213 days. The screening window will be no greater than 30 days prior to Day 1 (administration of IP). Plasmapheresis will be performed on Day 22 and Day 57 with an EOS phone call on Day 183.

3.2 Schematic Diagram of Study Design

Figure 2 EBSI-CV-317-010 Schematic Diagram of Study Design

Note: Days 29, 64, and 183 are phone calls

3.3 Description of Study Assessments

The underlying subsections (Section 3.3.1 through Section 3.3.13) describe the planned study procedures and assessments. For the per visit timing of these procedures and assessments refer to Section 5.2 and the study Schedule of Events. Information on subject consent is described in Section 11.1.

3.3.1 Review of Eligibility Criteria

Review of inclusion and exclusion criteria should be completed, and subject eligibility confirmed prior to planned vaccination and plasmapheresis procedures. Refer to Section 4.1 and Section 4.2 for criteria.

3.3.2 Medical History and Demography

Medical history information will be collected from subjects at the Screening Visit and confirmed at the Day 1 Visit (at baseline i.e., prior to IP administration) and will include (but not be limited to) demographic information (date of birth, race, ethnicity, and sex of subject), current and past medical conditions (including presence of joint pain), prior and concomitant medications (see Section 5.3) taken within 30 days of Screening Visit (or within 90 days for blood products, or within 6 months for immunosuppressive/immunomodulatory medications).

3.3.3 Physical Examination

A complete physical examination will be performed on subjects during the Screening Visit. The examination should include, general appearance, eyes-ears-nose-throat, head-neck, lungs-chest, heart, abdomen, musculoskeletal, lymph nodes, skin, extremities, and neurological assessment.

A targeted physical exam may be performed on subjects at additional time points if indicated by AE, SAE, or Adverse Event of Special Interest (AESI) reports.

3.3.4 Vital Signs

Vital signs collected from subjects will include blood pressure, heart rate, respiratory rate, and temperature. The first set of screening vitals are to be collected and transcribed into the screening electronic Case Report Form (eCRF) for inclusion of the subject into the study. Repeat measurements on abnormal vital parameters are allowed twice for confirmation of eligibility to receive the vaccination. Vital signs will be taken prior to and after study vaccine administration and should be within normal limits prior to planned vaccination.

Measurement of body weight, height for body mass index (BMI) calculations will be obtained at the Screening Visit.

3.3.5 Laboratory Tests

At the Screening Visit, blood samples will be collected for serum testing for HBsAg, HCV antibody, HIV-1/HIV-2 antigen/antibody (Ag/Ab), and CHIKV IgG antibodies, and urine will be collected for pregnancy testing for women of childbearing potential (CBP).

For additional information on sample collection, processing, storage, and shipment refer to the study Laboratory Manual.

3.3.6 Immunogenicity Sample

Anti-CHIKV SNA levels will be assessed using a validated CHIKV-luc assay that measures neutralization titer of 80% (NT₈₀). CHIKV IgM and IgG levels will be assessed by serum ELISA and PBMCs by assays performed on whole blood. Blood samples will be taken on Day 1 (prior to IP administration), Day 8, Day 15, Day 22, and Day 57 (or at Early Discontinuation/Withdrawal). For information on the immunogenicity assessment see Section 6.1.

For additional information on sample collection, processing, storage, and shipment refer to the study Laboratory Manual.

3.3.7 Pregnancy Testing and Contraception

Female subjects of CBP will undergo a urine pregnancy test at the Screening Visit and prior to IP administration on Day 1, prior to plasmapheresis on Day 22 and Day 57, and at any Early Discontinuation Visit. The subject must have a negative urine pregnancy test on Day 1, prior to administration of IP, and prior to both plasmapheresis visits.

Women of CBP must also use an acceptable method of contraception from prior to Day 1 through the Day 183 EOS Visit. Acceptable methods include highly effective forms of contraception such as: hormonal contraceptives (e.g., implants, pills, patches) containing combined estrogen and progestogen, or progestogen-only initiated ≥ 30 days prior to dosing **or** IUD inserted ≥ 30 days prior to dosing **or** use of double barrier type of birth control (male condom with female diaphragm, male condom with cervical cap). The Investigator must confirm that contraception methods (e.g., hormonal contraceptive or intrauterine device) were initiated ≥ 30 days prior to Day 1 to be considered fully effective.

The Investigator must report any pregnancies as described in Section 7.3.1.

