3.4 End of Study

An individual subject is considered to have completed study participation after completion of the Day 183 visit and any required safety follow-up.

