4 SELECTION AND WITHDRAWAL OF SUBJECTS

4.1 Subject Inclusion Criteria

Subjects must meet all the following criteria to be enrolled:

1. Able and willing to provide informed consent voluntarily signed by subject
2. Any gender, 18 to 45 years of age (inclusive).
3. Generally healthy, in the opinion of the Investigator, based on medical history, physical examination and screening laboratory assessments.
4. Women who are either:
 - i. Not of CBP: pre-menarche, anatomically sterile, or post-menopausal (defined as ≥ 12 months without menses).

or:

 - ii. Meeting all the below criteria:
 - Negative urine pregnancy test at screening visit **and**
 - Negative urine pregnancy test immediately prior to dosing at Day 1 **and**
 - Using an acceptable method of contraception (if female of CBP) for the duration of participation, such as:
 - Hormonal contraceptives (e.g., implants, pills, patches) initiated ≥ 30 days prior to dosing or
 - Intrauterine device (IUD) inserted ≥ 30 days prior to dosing or
 - Double barrier type of birth control (male condom with female diaphragm, male condom with cervical cap).

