5.2.9 Day 183 (-14/+7d) Telephone Contact for Visit 9 End of Study

- SAE and AESI evaluation
- Review concomitant medications (only if associated with SAE or AESI)

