5.2.10 Early Discontinuation/Withdrawal Visit

All subjects who discontinue study participation before the Day 57 visit will be requested to undergo an Early Discontinuation/Withdrawal Visit. The following will be conducted:

- Review AEs, AESI and SAEs
- Review concomitant medications associated with new or ongoing AEs and any AESIs or SAEs
- Blood collection for anti-CHIKV SNA, ELISA, PBMC
- For women of CBP: urine pregnancy test

If the visit occurs within 7 days after study vaccine administration, the following will also be conducted:

- a. Review of the memory aid
- b. AE (solicited) evaluation

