7.3 Reporting Requirements for Immediately Reportable Events

7.3.1 Principal Investigator's Reporting Requirements

The following events must be reported within 24 hours of awareness by the Principal Investigator (or designee) to Sponsor's Medical Monitor and Global Pharmacovigilance Department (Global PV):

- Any SAE regardless of causal association with the IP.
- Any AESI regardless of causal association with the IP.
- Confirmed pregnancy of female subjects.

The appropriate form(s) (listed below) will be completed and sent by email to the following address:

[REDACTED]
Emergent BioSolutions Inc.

Email: [REDACTED]

Telephone (toll free): [REDACTED]

For SAE/AESI, the “Serious Adverse Event/Adverse Event of Special Interest Report Form” will be completed (abbreviated hereafter as “SAE/AESI Report Form”). The SAE/AESI Report Form is **not** the same as the AE eCRF. Supporting documentation that may be emailed to accompany the form(s) can include source documentation or medical records (e.g., discharge summary for hospitalizations, lab reports) which support a diagnosis. Participant identifiers (e.g., name, address, telephone number, social security number, medical record number, or hospital/laboratory number) must be redacted from the source documentation. All SAEs that are unexpected (e.g., adverse drug reactions) must be reported to the Institutional Review Board (IRB) by the Investigator (or designee) as required by ICH GCP E6.

If a subject becomes pregnant during a study, the Sponsor will be notified. All pregnancies where conception occurred after first exposure to the IP through the EOS visit are to be followed to outcome (e.g., delivery, spontaneous/elective/therapeutic abortion), including after the study is completed and even if the participant is withdrawn from the study. If a pregnancy results in an abnormal outcome that the reporting health care professional considers might be due to the study drug, then the guidelines for expedited reporting of serious, unexpected adverse drug reactions (SUSAR) should be followed (see Section 7.3.2).

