Any pregnancy that occurs during study participation must be reported using clinical study pregnancy forms (“Pregnancy Notification Form” and “Pregnancy Follow-up Form”). To ensure subject safety, each pregnancy must be reported to the Sponsor within 24 hours of learning of its occurrence. The pregnancy must be followed up to determine outcome (including premature termination) and status of mother and child. Pregnancy complications and elective terminations for medical reasons must be reported as an AE or SAE.

Spontaneous abortions must be reported as an SAE.

Any SAE occurring in association with a pregnancy brought to the Investigator’s attention during or after the subject has completed the study and considered by the Investigator as possibly related to the study treatment, must be promptly reported to the Sponsor.

The Investigator is responsible to notify their IRB according to their policy.

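### Conceptions are to be followed to outcome through Day 183, but after Day 57 no scheduled contact asks about pregnancy, so capture of an uncomplicated pregnancy is passive

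*Protocol*

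**What the plan says.** **The obligation runs to Day 183.** Protocol 4.1, criterion 4.ii, makes contraception an entry condition: "Using an acceptable method of contraception (if female of CBP) for the duration of participation, such as". Section 3.4 fixes the end of participation: "An individual subject is considered to have completed study participation after completion of the Day 183 visit and any required safety follow-up". Section 3.3.7 names the same end point: "Women of CBP must also use an acceptable method of contraception from prior to Day 1 through the Day 183 EOS Visit". On reporting, 7.3.1 says "All pregnancies where conception occurred after first exposure to the IP through the EOS visit are to be followed to outcome" and "each pregnancy must be reported to the Sponsor within 24 hours of learning of its occurrence". SAP 9.4.1 and Listing 16.2.8.3.2 provide for a listing of pregnancy outcomes.

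**Scheduled ascertainment ends at Day 57.** After dosing, 3.3.7 places the tests "prior to plasmapheresis on Day 22 and Day 57, and at any Early Discontinuation Visit". The Schedule of Events, in both Protocol and SAP, marks the last test and the last inclusion/exclusion recheck at Day 57. Sections 5.2.8 and 5.2.9 give the Day 64 and Day 183 calls two items each: SAE and AESI evaluation, and "Review concomitant medications (only if associated with SAE or AESI".

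**Early withdrawal is described in two ways.** Section 5.2.10 says "All subjects who discontinue study participation before the Day 57 visit will be requested to undergo an Early Discontinuation/Withdrawal Visit", and footnote 2 of the Schedule confines the test at that visit to departures before Day 57. Section 4.3.1 instead counts any stop before Day 183 as early withdrawal and has the investigator ask the subject to attend a visit. Section 4.3.3 extends the same outreach to withdrawals in the follow-up period.

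**The concern.** The protocol commits to following vaccine-exposed conceptions over the whole of participation, but the visit content that would reveal them stops well before that. A site that performs every listed item at Day 64 and Day 183 complies fully and never asks about pregnancy or contraception. The items it does ask about would not normally reveal an uncomplicated pregnancy. Such a pregnancy meets none of the SAE criteria in 7.1.5, and the only AESI (7.1.4) is medically attended arthralgia. General medication collection ends at Day 29 (5.3), so a stopped contraceptive is not recorded either.

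What is at stake is the completeness and balance of the pregnancy outcomes listing. Section 7.3.1 requires spontaneous abortion to be reported as an SAE, so the Day 64 and Day 183 questions can bring out adverse outcomes while uncomplicated pregnancies depend on the subject mentioning them. A listing built that way would lean toward adverse outcomes.

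**Working it through.** The plan states no figure for this gap. The one related figure, a per-subject duration of 213 days (3.1.3), reproduces as 30 days of screening + 183 = 213, so the visit days are consistent.

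**Length of the interval** (days and windows from the Schedule of Events):
- Dosing to end of study: 183 − 1 = 182 days.
- Last scheduled test to end of study: 183 − 57 = 126 days; 126/182 = 69%.
- Shortest with windows: last test at Day 57 + 5 = 62, final call at Day 183 − 14 = 169; 169 − 62 = 107 days; 107/168 = 64%.
- Longest with windows: last test at Day 57, final call at Day 183 + 7 = 190; 190 − 57 = 133 days; 133/189 = 70%.

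**What each contact can detect:**

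| Contact | Pregnancy test | Eligibility recheck | Events asked about | Medications asked about |
|---|---|---|---|---|
| Day 22 | yes | yes | unsolicited AE, SAE, AESI | all |
| Day 57 | yes | yes | SAE, AESI, AEs within 30 minutes of plasmapheresis | SAE/AESI-linked |
| Day 64 call | no | no | SAE, AESI | SAE/AESI-linked |
| Day 183 call | no | no | SAE, AESI | SAE/AESI-linked |

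**Expected numbers.** The documents give neither the number of women of childbearing potential nor a pregnancy rate. As an assumption, take 8 to 20 such women and 1% to 10% pregnancies per woman-year. Expected count = women × rate × 126/365.25.
- Low: 8 × 0.01 × 0.345 = 0.03.
- High: 20 × 0.10 × 0.345 = 0.69.

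**Early withdrawal.** There are two readings.
1. If 5.2.10 governs, the visit exists only for departures before Day 57. A test at every such visit (3.3.7) and a test only before Day 57 (footnote 2) then agree.
2. If 4.3.1 and 4.3.3 govern, the visit extends to Day 183. Section 3.3.7 then requires a test after Day 57 that footnote 2 excludes.

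The root conflict is therefore 4.3.1 and 4.3.3 against 5.2.10. Whether 3.3.7 clashes with footnote 2 depends on how that is settled.

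**The case against.** The strongest reply is that no rule is broken. The 24-hour duty starts when the site learns of a pregnancy, so not asking cannot breach it, and passive capture is a workable choice. That stands: a reader might infer that the plan violates its own reporting requirement, and the documents do not support this.

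A reader might also infer that a woman who leaves after Day 57 has no early withdrawal visit. The documents do not settle that. Sections 4.3.1 and 4.3.3 imply such a visit, 7.5.2 mentions Early Withdrawal visits alongside Day 183, and only 5.2.10 limits the visit to before Day 57.

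The 69% might be read as the share of pregnancies missed. It is calendar time only. Few or no pregnancies are expected, the listing is produced only if applicable, pregnancy is not among the safety endpoints in SAP 3.2, and serious adverse outcomes have a route in through SAE questioning. All of this limits the importance of the point.

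Other provisions help less. Ongoing compliance monitoring (5.4) is general and names no pregnancy or contraception check. Unscheduled visits (5.2.11) permit a test but do not prompt one. The 24-hour telephone number (7.2) is for untoward reactions. Pregnancy is a coded withdrawal reason (4.3.4), but that too needs the site to know. Tying the tests to plasmapheresis explains why testing stops at Day 57, but not why no question is asked afterwards.

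The eCRF, its completion guidelines and the consent form are not available here and may contain a prompt. The point is limited to what the Protocol and SAP list.

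**Conclusion.** The point holds as a gap in data capture. For a nominal 126 of 182 post-dose days (69%; 107 to 133 days with windows), the protocol wants conceptions followed to outcome but lists no procedure that would identify an uncomplicated one. The practical size is small: between 0.03 and 0.7 expected pregnancies under the assumed ranges. Immunogenicity sampling ends at Day 57, so no immunogenicity endpoint is affected. It still merits correction because, with so few subjects, one unreported pregnancy could be the only one, and the route that remains open favours adverse outcomes. The conclusion assumes that sites do what the visit lists say and no more. The inconsistency over early withdrawal visits is a separate matter and stands whatever is decided about the calls.

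**What to change.** 1. For women of childbearing potential, add a pregnancy-status data-capture question to the Day 183 call (5.2.9) and to any withdrawal contact after Day 57, with matching entries in the Schedules of Events. Adding it at Day 64 is optional and yields little one week after the Day 57 test. Route positive answers to the existing 7.3.1 pregnancy forms and Listing 16.2.8.3.2.
2. If the sponsor prefers passive capture, say so in 7.3.1 and qualify the listing accordingly.
3. Reconcile 4.3.1 and 4.3.3 with 5.2.10 on who is asked to attend an early withdrawal visit, then 3.3.7 with footnote 2 on testing at that visit. Which testing or contraception rule should apply is for the sponsor and is not proposed here.

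The cost is a small eCRF field and a minor protocol amendment with the IRB approval that 12.2 requires. The Day 64 and Day 183 calls are already planned and no test is added, but a withdrawal contact after Day 57 may be an extra call. A question at Day 183 cannot reveal a conception the subject does not yet know of, so it narrows the gap without fully closing it.

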3.3.8 Investigational Product Administration

Investigational Product is 0.8 mL in volume and administered by IM injection into the deltoid muscle with a field-formulated syringe attached to 25 gauge 1" (or 1.5") needle, using universal precautions and sterile technique in accordance with General Best Practice Guidelines for Immunization: Best Practices Guidance of the Advisory Committee on Immunization Practices (ACIP) (27) per Table 1.

Table 1 Needle Length for IM Injections by Sex and Weight

Sex, Weight	Needle length	Injection Site
Men and women, <60 kg (<130 lbs)	1 inch (25 mm)	Deltoid muscle of arm
Men and women, 60-70 kg (130-152 lbs)	1 inch (25 mm)	
Men, 70-118 kg (152-260 lbs)	1-1.5 inches (25-38 mm)	
Women, 70-90 kg (152-200 lbs)		
Men, >118 kg (260 lbs)	1.5 inches (38 mm)	
Women, >90 kg (200 lbs)		

Source: Adapted from Table 6-2, General Best Practice Guidelines for Immunization: Best Practices Guidance of the Advisory Committee on Immunization Practices (ACIP) (27).

Investigational Product is to be administered by a staff member only under the direct supervision of the Investigator or a qualified sub-Investigator identified on the FDA Form 1572. Under no circumstances will the Investigator allow PXVX0317 vaccine to be used other than as specified in the protocol.

For further details on the IP refer to Section 5.1.

3.3.9 Acute Observation After IP Administration

The subject will be monitored by study staff for signs of an acute adverse reaction for 30 minutes after injection and vital signs will be obtained at least 30 minutes and no longer than 60 minutes after injection.

3.3.10 Solicited Adverse Events

Solicited AEs will be collected from IP administration until Day 8. Solicited AEs for this study are local events of pain, redness, and swelling at the injection site and systemic events of oral temperature $\geq 38^{\circ}\text{C}$ (≥ 100.4 degrees Fahrenheit [$^{\circ}\text{F}$]), chills, fatigue, headache, myalgia, arthralgia, and nausea (see Section 7.1.2 and Section 7.1.2.1).

Subjects will be trained to complete a memory aid to observe, measure, and record these solicited AEs. To measure oral temperature, a digital thermometer will be provided to the subject to measure their temperature each day and record them in their memory aid. To record injection site local reactions, a ruler will be provided to the subject to measure and record the diameter of redness and swelling at the largest point of the reaction each day.

Study staff will review the signs and symptoms recorded in the memory aid. The Investigator will then assess all solicited AEs for severity (Section 7.1.7) and the action taken, and causality (Section 7.1.8). The results of the Investigator's assessment will be recorded as a separate source document and will be entered on the solicited AE CRF. Symptoms continuing beyond the solicited AE collection period will be collected and recorded on the AE CRF.

Details on definition, evaluation, reporting periods and documentation are outlined in Section 7.

